9.4 Secondary Efficacy Analysis Methods

9.4.1 General Approach

As outlined in the above sections, the secondary outcome variables comprise a combination of binary, ordinal, and continuous measures that are collected at 6-month intervals through post-operative Month 24 and at either 6- or 12-month intervals thereafter. These outcome measures will be summarized in both tabular and graphical fashion by treatment arm over the full follow-up period, although the focus of the analysis will be on the first 36 months of the post-operative period. We will then use model-based approaches appropriate for the variable type (linear mixed models for continuous variables and GEE extensions of robust Poisson regression models for binary outcomes) to compare the outcomes for the two treatment arms across time.

Because the primary scientific interest for the study is in the trajectories of various the outcomes across time and because information about the patterns of these trajectories is limited, a longitudinal approach incorporating all time points will generally be employed. Specifically, the unit of analysis will be the participant visit, where visits are defined as in Section 4.5 starting 6 months post operatively, and the models will incorporate treatment group, time, and treatment group by time, as well as site, the randomization stratification variable, as fixed effects in the model with time (or visit) will be treated as a categorical variable to incorporate the expected non-linearity of time effects. Participant will be included as a random effect in the linear mixed model with an assumed compound symmetric covariance structure across the post-operative observation period and this same compound symmetric structure will be assumed in the GEE model with observations clustered within participant. The general structure of the SAS code that will be used for the mixed model (using the POPDI-6 as an example) is summarized below.

Proc Mixed data=SUPeR;

WHERE visit le 36; *** Constrains analysis to first 36 months of follow-up;
Class treatment visit center participant;
Model POPDI-6=treatment visit treatment*visit center/solution;
Random participant;
Lsmeans treatment*visit/ pdiff Cl;
Contrast 'POPDI Outcome' treatment 7 -7 treatment*month 111111111-1-1-1-1-1;

As suggested by the SAS code, the primary hypothesis will be tested using the F-test from the Contrast statement, which tests whether mean POPDI across 36 months differs for the two treatment arms. Note that the LSMEANS statement will provide by visit estimates of the post-operative POPDI6 score for each treatment arm from Month 6 through Month 36. These estimates will allow a description of the difference in trajectory of treatment effect in the two arms and will provide descriptive measures of differences between the two arms at each study visit. If the outcome is binary rather than continuous, the SAS procedure GENMOD will be used with a Poisson distributional assumption to generate comparable comparisons between the treatment arms in which the difference is assessed using a relative risk rather than mean difference metric.

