8.4 Demographic and Baseline Characteristics

Demographic and baseline clinical characteristics for the study participants will be summarized by study arm using the general analysis rules describe above. Variables of interest include: age (years), parity, gravidity, race and ethnicity, marital status, education level (classified as binary variable as having some college or greater or no college education), health insurance status (private only, Medicare/Medicaid only, combination of both), smoking status (never, previous, current), prior prolapse surgery, BMI, and baseline levels of all QOL measures.

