9.4.3 Comparison of Functional Measures of Treatment Efficacy

A second component of the secondary efficacy aim for this study is to compare multiple functional and quality of life for the two treatment regimens. As outlined in Sections 3.2 and 9.2, outcomes associated with this aim will include a number of continuous (e.g., scales from the PFDI-SF, PFIQ-SF, PISQ-R and SF-12 scales) and binary indicators (global improvement and de novo risk of voiding dysfunction, incontinence, dyspareunia). While the analyses for these secondary outcomes will produce point and interval estimates as well as p-values from hypotheses, all analyses are considered to be descriptive rather than inferential, so p-values will be interpreted as measures of evidence of descriptive differences in the treatment arms, not formal inferences.

Analyses for the continuous outcome measures associated with this efficacy aim will be analogous to those described above. For these continuous secondary outcomes, additional models that account for covariates found to be potentially confounded with treatment in the preliminary descriptive analysis

(specifically any baseline or clinical values found to be associated with treatment at the 0.10 level) will be fit to ensure that these potentially confounding effects don't change treatment effect conclusions.

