The SF-6D preference-based utility index algorithm derived from the SF-12 instrument53 will be used to calculate each participant's utility index at baseline and various follow up time points based on her responses to the SF-12 questionnaire. The SF-6D focuses on seven of the eight health domains covered by the SF-12: physical functioning, role participation (combined role-physical and role-emotional), social functioning, bodily pain, mental health, and vitality.). This instrument has been previously used in women with urinary incontinence54. These data will be used to compare change in QALYs between the two treatment groups. We are choosing to use a general scale to calculate change in utilities (rather than condition-specific) to allow for comparison of cost-effectiveness results with other interventions and diseases. Because the follow up period for participants spans at least three years, costs and QALYs in the second year and third year of follow up will be discounted using a 3% discount rate/year.

Differential mean costs and differential mean QALYs between the two treatment groups will be estimated using multiple regression analysis. Specifically, a generalized linear model with appropriate link function (e.g., log-link) and response probability distribution (e.g., gamma distribution) will be used to analyze costs due to the potential skewness and heteroscedasticity of medical expenditure data, while an ordinary least squares regression will be used for analyzing QALY data. The models will account for treatment group, study site and stratification factors, as well as other characteristics of the participants that are found to differ significantly between the traditional vaginal hysterectomy with native tissue vault suspension and mesh hysteropexy suspension groups. When estimating QALYs, we will also adjust for participants' baseline utility scores to account for potential imbalance in baseline utility between the two treatment groups.55

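### The main mixed model for the secondary scales leaves out each scale's own baseline value, and its 7 -7 contrast cannot be estimated on the stated Month 6 to 36 visits.

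*SAP*

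**What the plan says.** SAP Section 9.4.1 sets out one linear mixed model for the continuous secondary outcomes, with POPDI-6 as the worked example. Text and code agree on the fixed effects: treatment, visit, their interaction and site ("Model POPDI-6=treatment visit treatment*visit center/solution"). The text says that "visits are defined as in Section 4.5 starting 6 months post operatively", so baseline is neither a response nor a covariate. The WHERE line in the code caps the data at Month 36 and sets no lower limit.

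The test is then named: "the primary hypothesis will be tested using the F-test from the Contrast statement" (here the hypothesis for the secondary scale, not the trial's primary endpoint). The contrast is coded "treatment 7 -7 treatment*month", and the by-visit estimates are to run "for each treatment arm from Month 6 through Month 36".

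Baseline values appear in three other places:
- Section 8.4 tabulates "baseline levels of all QOL measures".
- Section 9.4.3 adds covariates to extra models if they pass a screen: "specifically any baseline or clinical values found to be associated with treatment at the 0.10 level".
- Section 9.4.5 adjusts QALYs, with no screen, for "baseline utility scores to account for potential imbalance in baseline utility between the two treatment groups".

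The PISQ-IR subscales in Section 9.2 are already changes from baseline, and catheter duration has no baseline, so neither is part of the baseline point. The ten PISQ-IR definitions compute that change at Month 1, while also saying that scores are taken every six months.

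**The concern.** A pre-surgery score usually carries some information about the post-surgery score. Putting it in the model reduces residual variance at no cost, because the data are already collected. The plan instead lets baseline in only when the arms happen to differ on it. That rule responds to chance imbalance, and a strongly prognostic baseline that is well balanced would never be used.

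The contrast problem is one of execution. The plan rests its test on a contrast that does not fit the visits it describes, and that names a treatment-by-month effect where the model has treatment by visit. Whoever programs it must change either the weights or the visit set. One way to make 7 -7 run for POPDI-6 is to keep the baseline and 6-week rows, which would average a pre-surgery score into the treatment effect.

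**Working it through.** **Visit count.** From the schedule in SAP Section 4.5 (protocol Table 4), between Months 6 and 36:
- PFDI-20, and likewise PFIQ, SF-12 and the activity scale: Months 6, 12, 18, 24, 36, so k = 5. Protocol Section T confirms that Month 30 is an abbreviated visit.
- POPQ: the same plus Month 30, so k = 6.

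**Estimability.** Write the mean for arm i, visit j, site c as m + a_i + b_j + g_ij + s_c. The arm difference in the equally weighted mean over k visits, multiplied by k, is k(a_1 − a_2) + Σ_j (g_1j − g_2j). With interaction weights of +1 and −1, the treatment coefficient must therefore equal k. A rank check on the full design (2 arms, 8 sites) gave:

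| Visits | 7 -7 | k -k |
|---|---|---|
| k = 5 | not estimable | estimable |
| k = 6 | not estimable | estimable |
| k = 7 | estimable | estimable |

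For POPDI-6, seven levels arise only by adding baseline and 6 weeks, which the open-ended WHERE line would allow but the text excludes. If the true effect were zero at baseline and constant afterwards, the contrast would then recover 6/7 of it, a shrinkage of 1/7 or 14%. Seven would still not be general: PFIQ and SF-12 have no 6-week assessment, so they would have six levels. The interaction weights read from the PDF are irregular. That may be damage in reading the file, and nothing here depends on it.

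**Precision lost.** The documents give no correlations, so these are assumptions: baseline to follow-up r_b, between follow-up visits r_w, compound symmetry as in Section 9.4.1. In SD² units:
- variance of the k-visit mean: v = (1 + (k − 1) r_w)/k
- share removed by adjusting for baseline: r_b²/v

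| k | r_b | r_w | v | Share removed |
|---|---|---|---|---|
| 5 | 0.1 | 0.7 | 0.76 | 0.01/0.76 = 1.3% |
| 5 | 0.2 | 0.7 to 0.5 | 0.76 to 0.60 | 5.3% to 6.7% |
| 5 | 0.3 | 0.7 to 0.5 | 0.76 to 0.60 | 11.8% to 15.0% |
| 5 | 0.4 | 0.6 | 0.68 | 0.16/0.68 = 23.5% |
| 5 | 0.5 | 0.5 | 0.60 | 0.25/0.60 = 41.7% |
| 6 | 0.1 | 0.7 | 0.75 | 0.01/0.75 = 1.3% |
| 6 | 0.4 | 0.6 | 0.667 | 0.16/0.667 = 24.0% |
| 6 | 0.5 | 0.5 | 0.583 | 0.25/0.583 = 42.9% |

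**Detectable difference.** The arm sizes of 88 and 87 come from the display shells in SAP Section 17. For 80% power with k = 5 and r_w = 0.6, the difference is 2.80 × √(v(1/88 + 1/87)):
- no baseline, v = 0.68: 0.349 SD
- r_b = 0.4, v = 0.68 − 0.16 = 0.52: 0.305 SD
- r_b = 0.1, v = 0.68 − 0.01 = 0.67: 0.347 SD

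At 0.4/0.6 the standard error is multiplied by √(1 − 0.235) = 0.874, equivalent to 1/0.765 = 1.31 times the women.

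**Screen and bias.** Under randomisation, a test at the 0.10 level passes about 10% of the time whatever the prognostic value. About 90% of the time the baseline score therefore enters no model through Section 9.4.3. A simulation at 0.4/0.6 with 88 and 87 women (8,000 runs, no true effect) gave a mean estimate of about 0 with and without baseline, a standard-error ratio of 0.878, and a screen pass rate of 10.0%.

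**The case against.** Section 7.7 calls all secondary analyses exploratory, and Section 9.4.3 calls the functional ones descriptive. No power claim or decision rule depends on these scales, and leaving out baseline does not bias them. This stands, and it limits the weight of the point.

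The gain may also be small. Every woman enters with prolapse beyond the hymen and a bothersome bulge, and surgery aims at a common anatomic result, so baseline may predict weakly. For point C, protocol Section B.2 notes that the structure measured after surgery is a cuff in one arm and a cervix in the other. This too is fair: at a correlation of 0.1 to 0.2 the gain is 1.3% to 7%. It is a reason to expect less, not a reason to discard data in hand.

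Section 7.2 offers a second route for baseline covariates, which also covers POPQ. That route depends on substantial differences between arms, so it has the same weakness as the 0.10 screen. The QALY adjustment is justified in the SAP by imbalance, not precision. It does show, however, that unconditional baseline adjustment is acceptable to the authors.

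On the contrast, the code is offered as a general structure, and Section 9.4.1 states the target in words as the mean over 36 months. Equal weights over the scheduled visits is the natural reading, and software would normally report a non-estimable contrast. For POPQ, Section 9.4.2 asks only for mean estimates by visit. These arguments make a silent error less likely. They do not settle which visits count, because text and code disagree on that.

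Month 1 is a drafting slip whose intent can be inferred.

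**Conclusion.** Both main points hold. The main model omits the own-baseline value for the PFDI-20 subscales, PFIQ, SF-12, activity scale and Ba, Bp and C, and the only other routes respond to chance imbalance. The cost is precision alone: 1.3% to 43% of the variance of the visit mean across the assumed correlations, and about 24% at 0.4/0.6, where the detectable difference would fall from 0.35 to 0.31 SD. At a baseline correlation of 0.1 it would stay at 0.35 SD. Those figures rest entirely on assumed correlations and compound symmetry.

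The 7 -7 contrast is not estimable on five or six visits; that conclusion needs no assumption beyond the schedule and the stated visit range. The matter should be corrected, but it does not touch the primary result, alpha or sample size.

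**What to change.** 1. In Section 9.4.1, make each outcome's own baseline value a covariate in the main model for the PFDI-20 subscales, PFIQ, SF-12, activity scale and Ba, Bp and C, whatever the 0.10 screen shows, and state a rule for missing baselines.
2. Restrict the data explicitly to Months 6 to 36. Write the contrast on the treatment-by-visit term with weights matched to the outcome: 5 -5 for the questionnaires and 6 -6 for POPQ.
3. In the PISQ-IR definitions, replace Month 1 with each scheduled visit (6, 12, 18, 24, 36, 48 and 60 months). Keep the change score among women with a matching baseline subscale, or state how a change in sexual-activity status is handled.

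The cost is SAP wording and code, with no new data. The one real decision concerns women whose sexual-activity status changes after surgery, since they have no matching baseline subscale. SAP Section 14, still blank, is the place to record the changes. If results by arm have already been seen, the baseline-adjusted model should be labelled accordingly; items 2 and 3 are needed either way. Protocol Section U ties the extension's methods to those used at 3 and 5 years, so an uncorrected specification would carry forward.

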9.4.2 Comparison of Anatomical Measures of Treatment Efficacy

One component of the first secondary efficacy aim is to compare anatomical measures of treatment efficacy across the two arms. For the 3 continuous measures (Ba, Bp, and C), the linear model described above will be used to generate mean estimates of each of these 3 metrics for the two treatment arms at each of the post-operative visits. For the binary measure of $C > \frac{1}{2}$ TLV, large-sample chi-square tests will be used to compare incidence at different time points.

9.4.3 Comparison of Functional Measures of Treatment Efficacy

A second component of the secondary efficacy aim for this study is to compare multiple functional and quality of life for the two treatment regimens. As outlined in Sections 3.2 and 9.2, outcomes associated with this aim will include a number of continuous (e.g., scales from the PFDI-SF, PFIQ-SF, PISQ-R and SF-12 scales) and binary indicators (global improvement and de novo risk of voiding dysfunction, incontinence, dyspareunia). While the analyses for these secondary outcomes will produce point and interval estimates as well as p-values from hypotheses, all analyses are considered to be descriptive rather than inferential, so p-values will be interpreted as measures of evidence of descriptive differences in the treatment arms, not formal inferences.

Analyses for the continuous outcome measures associated with this efficacy aim will be analogous to those described above. For these continuous secondary outcomes, additional models that account for covariates found to be potentially confounded with treatment in the preliminary descriptive analysis

(specifically any baseline or clinical values found to be associated with treatment at the 0.10 level) will be fit to ensure that these potentially confounding effects don't change treatment effect conclusions.

Analyses for the binary outcome measures associated with this efficacy aim will also be analogous to those described for the primary analyses in that they account for the longitudinal structure of the data, but they will be modified to account for the binary nature of the outcome measure and for any differences in outcome timing. Analyses will be conducted using a robust Poisson regression model as implemented through a generalized linear model with an assumed Poisson distribution and log link. The model structure will be comparable to that described above with each model including fixed effects treatment group, visit (as a categorical measure), treatment by visit interaction and, site. Participant will be handled as a clustering variable with an assumed compound symmetric covariance structure within participant. However, p-values and interval estimates of effect sizes will be obtained using GEE extensions of the generalized linear model using the Liang and Zeger sandwich estimator. For these outcomes, additional models that account for covariates found to be potentially confounded with treatment in the preliminary descriptive analysis (specifically any baseline or clinical values found to be associated with treatment at the 0.10 level) will be fit to ensure that these potentially confounding effects don't change treatment effect conclusions.

9.4.4 Predictors of Poor Treatment Effect

Two approaches will be utilized to evaluate predictors of poor treatment effect. First a binary outcome of treatment failure over a 36-month post-operative period will be created. Contingency tables and univariate logistic regression models will be used to determine whether this binary outcome is related to the potential predictors of advanced prolapse, age, obesity, smoking, menopausal status, estrogens, primary vs. recurrent prolapse, and physical and functional activity. Any covariates that are related to the outcome measure at a p-value of 0.10 will be utilized in a multivariable logistic regression model to develop an overall predictive model for treatment failure.

The second approach will involve fitting a multivariable complementary log-log model comparable to the model described in the Section 9.3 that includes the covariates described above with any covariates with a p-value of 0.10 or greater retained in the final model.

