Table 1. Vaginal Surgery Treatment Options for Uterovaginal Prolapse (non-obliterated procedures only)	2
Table 2. Uterosacral Vault Suspension Procedures	3
Table 3. Masking Summary	20
Table 4. Timeline of Measures	22
Table 5. Resource Utilization Data Collection and Price Data Source, by Utilization Category	26
Table 6. Body Image Scales	29
Table 7. Sample Size Calculations	30

A. Study Aims

The primary purpose of this randomized clinical trial is to compare the effectiveness and safety of two transvaginal apical suspension strategies for uterovaginal prolapse: a mesh augmented hysteropexy vs. vaginal hysterectomy and uterosacral ligament suspension.

A.1 Primary Aim

1. To determine whether treatment success in women with symptomatic uterovaginal prolapse undergoing transvaginal mesh augmented hysteropexy differs in women undergoing vaginal hysterectomy and native tissue cuff suspension at time points through 3 years.

Hypothesis –

1. This study will test the null hypothesis that treatment success will not differ in women with symptomatic uterovaginal prolapse undergoing vaginal surgery with a synthetic mesh hysteropexy compared to women undergoing vaginal hysterectomy with native tissue vaginal suspension against the alternative hypothesis that success does differ for the treatment regimens. Operationally, the hypothesis will be tested using a two-sided log-rank test to test for a difference in the risk of failure across the two treatment arms to achieve an overall Type I error rate of 0.05 across the interim and final analyses.

A.2 Secondary Aims

1. **Secondary Efficacy Outcomes:** To compare detailed anatomic and comprehensive functional outcomes (including prolapse, urinary, sexual, bowel and health-related quality of life (HRQOL)) in both groups.
2. **Safety:** To measure and compare safety, adverse events (including mesh erosion and exposure), pain, and need for subsequent procedures in both groups.
3. **Predictors of Poor Outcomes:** To determine if advanced prolapse, age, obesity, smoking, menopausal status, estrogens, previous prolapse surgery, and physical activity levels, alone or in combination, predict higher treatment failure.
4. **Cost-Effectiveness:** To compare the cost-effectiveness of the two surgical approaches and relate the difference in cost of care between the two groups to differences in health utilities and health-related quality of life.

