- 1) Women aged 21 or older who have completed childbearing
- 2) Prolapse beyond the hymen (defined as Ba, Bp, or C > 0 cm)
- 3) Uterine descent into at least the lower half of the vagina (defined as point C > -TVL/2)
- 4) Bothersome bulge symptoms as indicated on Question 3 of the PFDI-20 form relating to 'sensation of bulging' or 'something falling out'
- 5) Desires vaginal surgical treatment for uterovaginal prolapse
- 6) Available for up to 60 month follow-up
- 7) Amenorrhea for the past 12 months from either menopause or endometrial ablation
- 8) Not pregnant, not at risk for pregnancy or agree to contraception if at risk for pregnancy (only applicable to the rare endometrial ablation patient)
- 9) Eligible for no cervical cancer screening for at least 3 years^{40,41}

Exclusion Criteria

- 1) Previous synthetic material (placed vaginally or abdominally) to augment POP repair
- 2) Known previous uterosacral or sacrospinous uterine suspension
- 3) Known adverse reaction to synthetic mesh or biological grafts; these complications include but are not limited to erosion, fistula, or abscess
- 4) Chronic pelvic pain
- 5) Pelvic radiation
- 6) Cervical elongation defined as an expectation that the C point would be stage 2 or greater postoperatively if a hysteropexy was performed (note: cervical shortening or trachelectomy is not an allowed intraoperative procedure within the hysteropexy treatment group)
- 7) Women at increased risk of cervical dysplasia requiring cervical cancer screening more often than every 3 years (e.g. HIV+ status, immunosuppression because of transplant related medications, Diethylstilbestrol (DES) exposure in utero, or previous treatment for cervical intraepithelial neoplasia (CIN2, CIN3, or cancer))

Confidential Please Do Not Copy

- 8) Uterine abnormalities (symptomatic uterine fibroids, polyps, endometrial hyperplasia, endometrial cancer, or any uterine disease that precluded prolapse repair with uterine preservation in the opinion of the surgeon)
- 9) Indication for ovarian removal (adnexal mass, BRCA 1/2 positivity, family history of ovarian cancer)
- 10) Current condition of amenorrhea caused by exogenous sex steroids or hypothalamic conditions

F. Participant Screening

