220	0.94	0.98	0.99	>0.99			
240	0.96	0.98	0.99	>0.99			
260	0.95	0.99	0.99	>0.99			
280	0.98	0.99	>0.99	>0.99			
300	0.98	0.99	>0.99	>0.99			

Based on these calculations, a total of 180 participants will be randomized at a 1:1 ratio to the two treatment arms. This sample size will provide a power of 0.89 to detect an additive difference of 10% in the 2-year success rate (i.e. a hazard ration 0f 0.472) and a power of 0.99 to detect additive differences of 11% or greater in the 2-year success rate (hazard ratios of 0.423 or less).

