17 ATTACHMENTS

Potential Study Displays

Variable	Treatment Group		
	Native Tissue Hysterectomy N=	Mesh Hysteropexy N=	
RCT Consent	n	n	
Screen Failures	n	n	
Pre-Randomization Withdrawals	n	n	
Screen Failures and Pre- Randomization Withdrawals/RCT Consent (%)	xx.x%	xx.x%	
RCT Randomization	n	n	
Total Post-Randomization Withdrawals	n	n	
Completed Month 6	n	n	
Completed Month 12	n	n	
Completed Month 24	n	n	
Completed Month 36	n	n	
Completed Month 48	n	n	
Completed Month 60	n	n	

Table 1. Patient Disposition by Treatment Group

* p-value from Chi-square or Fisher's exact tests for treatment-group comparisons.

 Table 2: Baseline characteristics of the two arms

Measure	TVH	Hysteropexy	P value
Age in years			
Gravity			
Parity			
BMI (Kg/m ²)			
Menopausal status (almost everyone will be			
postmenopausal so we can just report % postmenopausal)			
Marital status			
Education			
Health Insurance			
History of smoking			
Current smoker			
Past history of surgery for SUI			
Past History of POP surgery			
Other Pelvic surgery			
Duration of POP symptoms			
History of recurrent UTI			
Yes to any PMH question e3 *			
POPQ Ba			
POPQ C			
POPQ Bp			
PVR (mean, median, IQR, usually has a right tail skewed			
distribution)			
PFDI -20			
POPDI-6			
UDI 6			
CRADI-8			
PFIQ			
ISI			
BIS			
PISQ-IR			
SF-12			
Functional activities score			
Pain scale score			
Number of pain medications (Mean number)			

Table 3: Efficacy Outcome Components Overall by treatment

Failure reasons	TVH	Hysteropexy	P value
Retreatment (n,%)			
Prolapse past the hymen only (n,%)			
Bulge symptoms only (n,%)			
Prolapse and Bulge symptoms (n,%)			

Table 3b: Efficacy Outcome over time by treatment

		Treatment Group			
			Vaginal		
		UPHOLD	hysterectom		
		Procedure	y and USLS	Total	P-
Characteristic	Statistic/ Category	(N=88)	(N=87)	(N=175)	value
12 Month Visit Outcome	Not Failure				
	Anatomic Failure				
	Anatomic and sympt.				
	Failure				
	Retreatment Failure				
	Symptomatic Failure				
24 Month Visit Outcome	Not Failure				
	Anatomic Failure				
	Anatomic and symp				
	Failure				
	Petreatment Failure				
	Symptomatic Failure				
26 Month Visit Outcome	Not Foilure				
So Month Visit Outcome	Not Fallure				
	Anatomic Failure				
	Anatomic and symp.				
	Failure				
	Retreatment Failure				
	Symptomatic Failure				

	Treatment Group				
			Vaginal		
		UPHOLD	hysterectom		_
-		Procedure	y and USLS	Total	.P-
Characteristic	Statistic/ Category	(N=88)	(N=87)	(N=175)	value

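### SAP 9.4.4, first approach: the one-at-a-time screen at p 0.10 inflates the odds ratios it keeps and hides the others; missing treatment arm and missing validation are separate gaps

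*SAP*

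**What the plan says.** Protocol A.2, item 3, asks whether the listed factors, "alone or in combination, predict higher treatment failure". SAP 9.4.4 answers this in two ways.

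**First approach.** "First a binary outcome of treatment failure over a 36-month post-operative period will be created". Each candidate is then examined by itself, by cross-tabulation and a single-factor logistic regression. There are eight candidates: "advanced prolapse, age, obesity, smoking, menopausal status, estrogens, primary vs. recurrent prolapse, and physical and functional activity". The rule for entering the joint model is: "Any covariates that are related to the outcome measure at a p-value of 0.10 will be utilized in a multivariable logistic regression model". The stated purpose is an overall predictive model. Treatment arm is not among the candidates, and no shrinkage, internal validation or correction for optimism is mentioned.

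**Second approach.** A multivariable complementary log-log model, described as comparable to the one in SAP 9.3, takes the same covariates with no univariate screen. The 9.3 model tests treatment, so arm is implied here but not stated.

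Three other places bear on the point:
- Protocol E, inclusion criterion 7, requires "Amenorrhea for the past 12 months from either menopause or endometrial ablation".
- The SAP 17 shell for Table 2 remarks of menopausal status: "postmenopausal so we can just report % postmenopausal".
- SAP 7.7 classes all secondary analyses as exploratory, with p-values given for description.

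**The concern.** The screen and the final estimates use the same small data set. A factor passes mainly when its observed effect is large, so the estimates that survive are too large on average. A factor that misses 0.10 never reaches the multivariable model and gets no adjusted estimate. The aim also asks about factors in combination, and a factor that matters only jointly with others can fail a one-at-a-time test.

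Two other omissions sit beside this. The planned treatment effect is a hazard ratio of about 0.47, yet arm is left out of a model meant to predict failure. And performance would be judged on the data used to build the model.

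At stake is how Aim 3 is reported: which factors are named, how strong they look, and how well the model seems to discriminate. The primary comparison is not affected.

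**Working it through.** **1. Expected failures.** The plan gives no failure count or power for this aim, so the count is derived from SAP 6 (exponential failure, 80% native-tissue and 90% mesh success at 24 months).
- Check on the inputs: ln(0.90)/ln(0.80) = 0.472, the SAP's own hazard ratio.
- Failure by 36 months: 1 − 0.80^1.5 = 0.284 (native tissue); 1 − 0.90^1.5 = 0.146 (mesh).
- With the arm sizes in the table shells: 0.284 × 87 + 0.146 × 88 ≈ 24.7 + 12.8, or about 38 of 175.
- SAP 6 plans for more: "a total of 180 participants will be randomized at a 1:1 ratio to the two treatment arms". That gives 90 × (0.284 + 0.146) ≈ 39.
- Range for 180 women: about 32 with 93% mesh success and 5% yearly loss; about 51 with 80% in both arms and no loss (180 × 0.284).
- Failures per candidate: 38/8 = 4.75.

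**2. What the threshold does by itself.** With eight independent null factors, the chance that at least one passes is 1 − 0.9^8 = 0.57.

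**3. Selection inflation.** The documents give no predictor effects, so these are assumed. The simulation used 175 women, eight independent factors, one with a true odds ratio of 1.3 per SD, the planned arm effect, 1,500 data sets per scenario and 4,000 new women for validation.
- Screened: the true factor is kept in 40% of trials, with an average odds ratio of 1.57 to 1.59 over repeat runs.
- Unscreened, with arm: average odds ratio 1.31 to 1.33.

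A second set-up with mostly binary factors and larger assumed effects shows the same pattern:

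| True OR | Dropped by the screen | Median OR when kept |
|---|---|---|
| 1.5 | 70–82% | 2.3–3.1 |
| 2 | 47–69% | 2.5–3.5 |
| 3 | 19–50% | 3.2–4.3 |

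In the unscreened model with arm, a true 2 is estimated at 2.1 to 2.2.

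**4. Separating screen from arm.** New-data AUC in the odds ratio 1.3 scenario:

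| | Without arm | With arm |
|---|---|---|
| Screened | 0.52 | 0.60 |
| All factors | 0.53 | 0.59 |

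Read down a column, the screen changes AUC by less than 0.01. Read across a row, arm adds 0.06 to 0.08.

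**5. Does omitting arm cause predictors to be dropped?** Arm is randomised, so it is independent of the baseline factors apart from chance. With true odds ratio 2, adding arm moved the chance of being kept only from 0.53 to 0.54 and the median kept odds ratio from 2.55 to 2.67. Optimism was 0.072 without arm and 0.074 with it. New-data AUC rose from 0.61 to 0.65.

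**6. Optimism (apparent minus new-data AUC).**

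| Assumed effects | Screened, no arm | All factors, no arm | All factors + arm |
|---|---|---|---|
| All null | 0.069 | 0.143 | 0.119 |
| One OR 1.3 per SD | 0.073 | 0.128 | 0.111 |
| Three OR 1.5 | 0.064 | 0.082 | 0.079 |

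**7. Bootstrap correction, all eight factors plus arm, ordinary fit (mostly binary set-up).** With true odds ratio 2: apparent 0.75, corrected 0.675, new data 0.66, calibration slope 0.55. With 1.5: apparent 0.715, corrected 0.64, new data 0.61, slope 0.44. The correction removes most of the excess but not all of it.

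**The case against.** The strongest reply is that the screen is blamed for too much, and most of that reply stands.

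- A reader might infer that dropping the screen would give a model that predicts better. Step 4 shows it would not: with arm held constant, new-data AUC hardly moves.
- A reader might infer that the screen is why the model looks better than it is. Step 6 shows the unscreened model is more optimistic. The causes are few events and no validation.
- A reader might infer that leaving out arm makes real predictors fall out. Step 5 shows it does not.
- Low detection is largely a sample-size limit. The factor with odds ratio 1.3 reaches p below 0.10 in 42% of unscreened models with arm, against 40% kept by the screen.
- A reader might infer that Aim 3 as a whole is compromised, or that clinical advice would be misled. SAP 9.4.4 has a second, unscreened approach, SAP 7.7 labels the work exploratory, and neither document proposes using the model for counselling.
- The effect sizes are assumptions, and at odds ratio 3 common factors are usually kept.

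The inflation of kept odds ratios and the missing adjusted estimates for dropped factors survive all of this. The exploratory label does not correct either. The second approach also does not fully cover the gap. Its retention rule, as printed, keeps terms with p at or above 0.10, and it refers to a complementary log-log model although SAP 9.3 now specifies a piecewise exponential one.

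**Conclusion.** The point holds for the first approach in SAP 9.4.4 only, as an optional improvement. There are three separate parts.

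1. **Screening.** Selecting and estimating on the same roughly 38 failures inflates kept odds ratios (1.3 per SD appears as about 1.6) and withholds adjusted estimates for the rest, against an aim that asks about combinations.
2. **Arm.** Its omission costs real discrimination, about 0.52 against 0.60 in new-data AUC. It is not the source of the selection bias. The gain depends on a treatment effect of the planned size and would vanish if the arms had equal failure rates.
3. **Validation.** Apparent AUC is about 0.07 too high under the planned rule. Removing the screen alone makes this worse, about 0.11 to 0.13 under small assumed effects.

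Menopausal status is close to constant by design and can contribute little as a predictor.

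The figures rest on the planning failure rates, independent candidates and assumed predictor effects. The direction of the inflation does not depend on the exact values: with about 56 failures and true odds ratio 2, 38 to 70% of real factors are still dropped and kept ones still look too strong (medians 2.35 to 3.4).

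**What to change.** In SAP 9.4.4, replace the first approach with one prespecified model for 36-month failure. It should contain the listed factors except menopausal status, plus treatment arm, and be fitted by penalised likelihood (Firth, for example). Report every coefficient with its interval, whatever its p-value, and a bootstrap optimism-corrected c-statistic beside the apparent one. Keep the contingency tables and univariate models as description, with no role in selection. State menopausal status as a percentage only, as the shell already suggests.

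The cost is SAP wording and a little analysis time; arm is already recorded. The downside is real: seven factors plus arm give 38/8 = 4.75 failures per parameter, or 38/9 = 4.2 if one factor needs two terms, so intervals will be wide. Dropping the screen brings no material gain in new-data AUC by itself. The benefits are less biased odds ratios, a full set of estimates and a more realistic performance figure. The figures for the unscreened model come from ordinary maximum likelihood; the penalised fit was not simulated.
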